6.1 CRITERIA FOR SUBJECT ELIGIBILITY

Patients eligible for this trial will be consenting recipients of related or unrelated stem cell allografts who have an active CMV infection or persistent CMV viremia despite 2 weeks of antiviral therapy or who cannot be maintained on antiviral agents due to therapy related toxicity. If the eligibility criteria are met and a patient is determined to derive benefit from infusion of CMVpp65-CTLs, a standard treatment consent will be obtained and the patient enrolled and treated on this clinical trial.

6.2 Subject Inclusion and Exclusion Criteria

6.2.1 Patient Inclusion Criteria

1. Each patient must satisfy at least one of the following criteria:

- a. The patient must have a clinically documented condition associated with CMV (e.g. interstitial pneumonia, hepatitis, retinitis, colitis)
Or
- b. The patient must have microbiological evidence of CMV viremia or tissue invasion as attested by viral culture, or detection of levels of CMV DNA in the blood or body fluids consistent with CMV infection.

2. Patient must also satisfy at least one of the following criteria:

- a. The patient's CMV infection is clinically progressing or CMV viremia is persistent or increasing (as evidenced by quantitation of CMV DNA in the blood) despite two weeks induction therapy with antiviral drugs.
Or
- b. The patient has developed CMV viremia as attested by viral culture, or detection of levels of CMV DNA in blood or body fluids while receiving prophylactic doses of antiviral drugs to prevent CMV infection post transplant.
Or
- c. The patient is unable to sustain treatment with antiviral drugs due to drug associated toxicities (e.g. myelosuppression [ANC < 1000/ μ l/ml without GCSF support] or nephrotoxicity [corrected creatinine clearance \leq 60 ml/min/1.73 m 2 or serum creatinine $>$ 2 mg/dl])

3. Patient has CMV specific T-cells from the donor of his/her HSCT available.

4. CMV infections are life threatening, and may involve multiple organ systems such as the lungs, liver, gastrointestinal tract, hematopoietic and central nervous systems. Antiviral drugs used for treatment may also compromise renal and hematopoietic function. Therefore, dysfunctions of these organs will not affect eligibility for this protocol.

5. Patients must meet the following clinical criteria to receive CMVpp65-CTL infusions

- a. Stable blood pressure and circulation, not requiring pressor support
- b. Evidence of adequate cardiac function as demonstrated by EKG and/or echocardiography.
- c. A life expectancy of at least 3 weeks, even if requiring artificial ventilation.
- d. There are no age restrictions

6.2.2 Patient Exclusion Criteria

- 1. Patients requiring high doses of glucocorticosteroids (\geq 0.3 mg/kg prednisone or its equivalent)
- 2. Patients who are moribund
- 3. Patients with other conditions not related to CMV infection (e.g. uncontrolled bacterial sepsis or invasive fungal infection) which are also life-threatening and which would preclude evaluation of the effects of a T-cell infusion.
- 4. Patients who are pregnant

6.2.3 Donor Inclusion Criteria

6.1.3a Donors in Group 1 (Historical Donors)

Donors in Group 1 (Section 5.1) would have already been determined to be eligible and will have donated blood or leukocytes to establish CMV-specific T-cells under IRB # 05-065, 07-055, 95-024, or 11-130. There are no additional eligibility requirements for these donors.

6.1.3b Donors in Groups 2 & 3 (Prospective and Volunteer Donors)

Transplant donors and healthy HLA typed volunteers who agree to provide T-cells for Third-party donation (section 5.1, Groups 2 and 3) will need to meet the following eligibility requirements prior to donation:

1. Donors must satisfy the criteria specified in FDA 21 CFR 1271.
2. Donors must be typed for HLA-A, B, C and DR
3. Donors must have a hemoglobin value > 10g/dl
4. Donors must be capable of undergoing, at least, a single standard 2 blood volume leukapheresis or a donation of one unit of whole blood

6.1.4 Donor Exclusion Criteria

1. HTLV/HIV(+) or Hepatitis B or C antigen(+) donors
2. Donors who are known CMV seronegative

7.1 RECRUITMENT PLAN

7.2 Recruitment Procedures

7.2.1 Patient Recruitment

Patients undergoing allogeneic HSCT who are eligible, will be recruited to this trial under the supervision of the allogeneic marrow transplant services in Medicine and Pediatrics.

Prior to receiving treatment, some patients may undergo diagnostic and/or other testing of their tissue, if available, to determine if their CMV infected cells are likely to respond to treatment with CMV specific T cells. Alternatively, blood samples may be required for research tests to ascertain that the CMV-specific T-cells do not contain any cells that could react against the patient. These patients will sign a separate pre-treatment consent.

Eligible patients will be interviewed prior to enrollment on this study, to explain the purpose and the involved treatments and procedures. The risks and benefits of participating in the trial and receiving CMVpp65-CTL infusions will be presented and discussed. These explanatory discussions will include a participating investigator and the patient. A non-participating family member or research nurse should be involved whenever possible.

7.2.2 Donor Recruitment

7.1.2a Donors in Group 1 (Historical Donors)

Because historical donors were only under the care of MSKCC for the period in which they donated cells for their primary recipients and have since returned home, they will be mailed a copy of the consent form to review during the consent discussion, which will occur over the phone. If they agree to 3rd party use of their cells, the consent will be signed and sent back via MSKCC provided pre-paid/addressed envelope.

The registration process is outline in section 15.1.

7.1.2b Donors in Groups 2 & 3 (Prospective and Volunteer Donors)

A similar but separate discussion that occurs with patients will also take place with the prospective donors of the T-cells, defining the risks of blood and/or white cell donations required for the generation of the T-cells to be used for adoptive immunotherapy, and the clinical indications for which the T-cells will be used. Following this discussion, the donor will be asked to sign a written consent to donate the blood cells to be used to generate CMVpp65-CTLs for adoptive immunotherapy.

7.2 Inclusion of Women and Minorities

Memorial Sloan-Kettering Cancer Center has filed form HHS 441 (re: Civil Rights), form HHS 641 (handicapped individuals), and form 639-A (re: Sex Discrimination). In selecting patients for study in the projects proposed in this protocol, we have taken due notice of NIH/ADAMHA policies concerning inclusion of women and minorities in clinical research populations. We expect that the study population will be fully representative of the range of patients seen at Memorial Hospital without exclusion as to age, gender, or ethnic background. Based on a January 1, 2001-December 2005 analysis of patient populations on allogeneic transplant protocols at this Center, the racial distributions were 24% African American, Hispanic or Asian, and 76% Caucasian. The gender distribution was 41% female and 59% male. The protocol is open to all patients irrespective of gender or ethnic background. The population of patients transplanted reflects the distribution of the patients in our tri-state referral area. However, it is anticipated that the distribution of patients by race and ethnicity will be the same for patients receiving marrow or PBSC transplants, but that a higher proportion of individuals from minority racial groups will be accrued to the cord blood transplant protocols, both because of the greater HLA disparity permissible and the concerted efforts of these banks to obtain donor units from populations underrepresented in the NMDP. Given the highly specific patient population that is subject/eligible for this treatment, the trial will be registered under clinical trials.gov to enable other transplant centers to review and refer patients for treatment. No other specific outreach efforts are planned for accrual.

Pregnant women are excluded from this study. There are no age restrictions for this study, and eligible children will be enrolled if appropriate consents are obtained from parents and /or guardians.

8.1 PRETREATMENT EVALUATION

Prior to T cell infusion, eligible and consenting patients will be clinically assessed for their general condition and for extent of CMV infection. Tests/exams will be obtained within 3 days of infusion (whenever possible). Certain tests may be omitted at the discretion of the treating physician:

- Clinical history and Physical examination
- Chest x-ray (not necessary if CT scan is done)
- CT scan is not required prior to treatment, but should be done, whenever possible, within 3 days of T cell infusion
- Ophthalmologic exam for CMV retinitis, if clinically indicated
- Colonoscopy for CMV colitis, if clinically indicated
- ECHO and/or EKG, if clinically indicated
- CBC with differential
- Comprehensive Panel
- Cultures of affected body fluids or tissues will be obtained whenever possible
- CMV viremia will be assessed by quantitation of CMV antigen+ blood leukocytes and by quantitation of CMV DNA in the blood by realtime quantitation PCR.
- Lymphocyte immunophenotype (BMT short panel) and T cell responses to PHA and Candida Albicans

In addition, T cell responses to CMV will be evaluated in [name] laboratory by:

- Assessment of T cell proliferation in response to CMV antigens and
- Quantitation of T cells generating IFNy in response to stimulation with a pool of CMV pentadecapeptides and
- In patients expressing HLA-A0201, B0701 or B0801 T cells binding CMV peptide – HLA A2, B7 or A24 tetramers
- Analysis of TCR V β repertoire will also be performed

9.1 TREATMENT/INTERVENTION PLAN

This is a single institution phase II trial designed to assess the therapeutic activity of primary donor derived CMVpp65 specific T-cells (CMVpp65-CTL) for the treatment of CMV infection or persistent CMV viremia after allogeneic hematopoietic stem cell transplantation. The T-cells will be generated from healthy, CMV seropositive donors by sensitization *in vitro* with autologous, cytokine-activated monocytes loaded with a pool of overlapping synthetic peptides spanning the sequence of CMV protein pp65.

9.1 Treatment with CMVpp65 Specific T-cells

Eligible patients who consent to enter this trial and for whom CMV-pp65 CTLs are available, will receive 3 weekly infusions of CMV-pp65 CTLs. The T cells will be administered immediately after thawing. The final product is cryopreserved in a volume of 1-2 ml. This will be drawn up in a sterile syringe containing 30 ml of normosol for intravenous administration and administered by slow intravenous infusion ideally over approximately 5 minutes.

In this phase II trial, patients will be treated at doses of 1×10^6 CMVpp65-CTL/kg/dose/week for 3 weeks (+/- 20% variability of total dose). Patients will be observed for the following 3 weeks. Additional 3 week courses of CMVpp65-CTL may be administered if levels of CMV DNA in blood are still detectable despite disease stabilization or improvement.

If the planned dose of CMV peptide sensitized T-cells is not achieved, but the cells generated exhibit required levels of CMV specific cytotoxic activity and meet all other release criteria, the T-cell product may be administered at a lower dose level.

In certain cases, in order to avoid refreezing of the final product to achieve a specific dose level, which may affect viability, variability of each dose may exceed +/-20%. In such cases, care will be given to ensure that the total combined volume of the 3 doses does not exceed the planned dose.

9.2 Subject Stratification

Subjects will include patients treated with CMVpp65-CTLs derived from their transplant donor. These will be patients with CMV seropositive transplant donors who have previously provided leucocytes for generation of CMVpp65-CTL and for whom such CMVpp65-CTL are available.

9.3 Selection of CMVpp65-CTL

Patients will be treated with CMVpp65-CTL generated from their transplant donor.

10.0 EVALUATION DURING TREATMENT/INTERVENTION

The timing of evaluations below is approximate. The schedule of tests described should be adhered to whenever possible. However, in certain situations, particularly late after treatment, circumstances may preclude assessments at the times specified, at which point they may be held at the discretion of the treating physician:

- Patients will be evaluated clinically by vital signs pre-infusion, post, and at approximately 1, 2, 3, and 4 following initiation of each infusion of CMV-specific T-cells
- The patient should be followed weekly for the first 8 weeks post-initial infusion with CMV-specific T-cells, then monthly until 6 months post initial infusion. Patients will receive interim history, review of systems, and physical exam (including GvHD evaluations) on the day of infusions, and on days 1, 8 and 15 whenever possible.
- Patients should be monitored by CBC and comprehensive metabolic panels weekly for the first 8 weeks post-initial infusion with CMV-specific T-cells, then approximately monthly until 6 months post initial infusion.
- Tests quantitating CMV viremia by CMV DNA copies per milliliter of blood should be obtained weekly for the first 8 weeks post-initial infusion with CMV-specific T-cells, then approximately monthly until 6 months post initial infusion
- Quantifications of T cells generating IFNy in response to pooled CMV pentadecapeptides or T cells specific for single pentadecapeptides known to be contained in the T cells infused should be measured weekly for the first 8 weeks post-initial infusion with CMV-specific T-cells, then monthly until 6 months post initial infusion. If the T cells infused are known to contain T cells that can bind specific CMV peptide/HLA tetramers, these T cells will also be quantitated.

- When possible, pre-initial infusion and at week 4 and month 6 post initial infusion, if >1% of the circulating T cells are found to be reactive against specific epitopes by either assay, these CMV-pp65-reactive T cells will, if possible, be characterized as to their T cell receptor V β repertoires, to determine whether and to what degree, the T cells expanding *in vivo* resemble (and, therefore, are likely to be derived from) the CMV-specific T cells infused at the time of adoptive transfer
- If there are clinical indications, research samples may be collected testing for cytokines.
- Flow Cytometry 7 panel to enable quantification of CD4 and CD8 T cell number may be obtained prior to the first infusion, on day 14, week 4, and week 8 post-initial infusion with CMV-specific T-cells, then monthly until 6 months post initial infusion
- T cell populations and their responses to mitogens and to candida albicans antigen should be obtained pre-initial infusion and may also be monitored at approximately 2, 4, and 6 months post initial infusion as a measure of general immune function.
- Patients with CMV pneumonia should be monitored by at least daily measurements of blood gases and/or O₂ saturations until normalized and weekly chest films together with CT scans at pre-infusion and approximately every 2-4 weeks until clear.
- Ophthalmologic evaluations will be made to document responses of CMV retinitis. These evaluations will ideally be done every 2 weeks.
- Patients with known CMV enteritis should be monitored by approximately three times weekly measurements of 24 hour stool volumes, stool guaiacs and cultures for CMV. If acceptable to the patient, colonoscopy should be repeated approximately three weeks after the dose of T cells to assess response.
- If the CMV infection affects the CNS, lung, or abdominal organs, and virus has been detected (e.g.: in pleural or peritoneal fluids), appropriate tissue and/or CSF may be collected (if indicated and possible) and tested for the presence of CMV and CMV specific T-cells. These tests should occur between 3-6 weeks post initiation of treatment, whenever possible.

APPROXIMATE SCHEDULE OF PATIENT EXAMINATIONS AND STUDIES

Evaluations	Pre-Infusion	Day 0 > 1	Day 7	Day 14	Day 15	Wk 3	Wk 4	Wk 5	Wk 6	Wk 7	Wk 8	Mo 3	Mo 4	Mo 5	Mo 6
History, Review of Systems, & Physical Exam (incl. GVHD eval) ¹	x	x	x	x	x	x	x	x	x	x	x	x	x	x	x
CBC/CMP	x	x	x	x	x	x	x	x	x	x	x	x	x	x	x
CMV PCR (10 ccs)	x	x	x	x	x	x	x	x	x	x	x	x	x	x	x
T cell Immunophenotype short panel	X			X			X				X	x	x	x	x
Mitogens (PHA)	X											X		X	
Antigen (Candida albicans)	X											X		X	
Research Bloods	X	x	x	x	x	x	x	x	x	x	x	x	x	x	x
Immune Monitoring ³	X		x	x		x	x	x	x	x	x	x	x	x	x
Chest X-Ray and/or CT (if indicated)	x														
EKG (if indicated)	x														
Ophthalmologic exam (if indicated)	x														
Colonoscopy (if indicated)	x														
Cultures of affected body fluids and/or tissue (if possible/indicated)	x					x									
Treatment CMV Specific T-cells ²		x	x	x											

¹ GVHD evaluations to be performed weekly until Week 8 and a consensus at Day 100

² If patient is given additional cycles of CMV specific T-cells, calendar will restart from Day 0. Doses are given weekly and can be held at the discretion of the PI or in the case of severe toxicity related to infusion.

³ Prior to and at specific intervals following infusion of CMVpp65-CTL, patients will be monitored for levels of CMVpp65-CTL in the blood as measured by quantitation of CTL precursor frequencies, CMV pp65-specific IFNy+ T-cells (35), or epitope specific-T-cells binding HLA-peptide tetramers and their V β usage (36). The third party T-cells will also be monitored by analysis of CMVpp65 IFNy+ T-cells as to their genetic origin.

11.0 TOXICITIES/SIDE EFFECTS

In this study, we will be capturing and tracking Grade 3-5 toxicities which occur within 30 days following an infusion of CMV infusion CTLs and are potentially attributable to treatment on study. We will also be capturing and tracking graft vs host disease occurring at any time point post-infusion. Patients who might subsequently receive donor lymphocytes, boosts, or a secondary transplant will be evaluable up until that time point. Toxicities which are attributable to underlying malignancy and/or were present prior to initiation of therapy will not be tracked. Please see section 17.2 for Serious Adverse Event reporting.

1. **Acute Toxicities and Transfusion Reactions.** The infusion of CMV-peptide specific T-cells might cause an acute transfusion reaction or an allergic reaction to the cell infusion manifested by any one or all of the following clinical signs and symptoms: fever, shaking chills, difficulty breathing, a drop in the blood pressure, skin rash or swelling of the mucus membranes in the mouth or vaginal tract, or impairment of kidney function. Based on prior experience with infusions of T-cells at our own and other

institutions, the risk of such immediate toxicities is anticipated to be small. However, each patient will be closely monitored for vital signs and clinical symptoms prior to and following T-cell infusion. Reactions will be treated as clinically indicated.

2. **Specific Immune Reactions.** The CMV peptide-specific T-cells are expected to migrate to sites where CMV infected cells are concentrated, and to begin to kill these CMV infected cell populations. These cells may be concentrated in the lung, liver, retina/central nervous system, or intestinal tract. While it is expected that the small doses of T-cells administered will take time to replicate, and will exert their antiviral effects over a time period of days to weeks, it is possible that these cells could concentrate in an infected tissue and cause more severe inflammation as they attack virus infected cells. This could transiently increase the severity of a pneumonia or a CMV –induced encephalitis, retinitis, hepatitis or intestinal infection, and could even be life-threatening. Additionally, patients with pre-existing pulmonary conditions maybe at increased risk for development of pulmonary toxicity including diffuse alveolar hemorrhage. For patients treated for drug resistant CMV-retinitis, these T cells could potentially cause partial or complete blindness. If this were the case, immunosuppressive drugs might be required to halt such a reaction, and eliminate the T-cells. Were this required, the antiviral activity of the T-cells would be removed and the infection could progress in the absence of any specific resistance.

3. **Graft versus Host Disease.** The CMV peptide-specific T-cells have been cultured for over 4 weeks. During this time, T-cells reactive against other antigens, including alloantigens that might be expressed by tissues in the patient, die off and are deleted. The T-cells to be infused will be tested and shown to have no significant activity against normal allogenic cells prior to their infusion. However, there is a finite risk that small numbers of alloreactive T-cells could be transferred in the T-cell inoculum, which could cause Graft versus Host Disease (GvHD). This immune reaction against the host can cause skin rash, hepatitis, and enteritis. In its most severe form, it can be fatal. Were moderate to severe GvHD (Grade 2-4) to develop, the patient will be treated with high doses of glucocorticosteroids. Additional immunosuppressive agents may be used if the GvHD does not respond to steroid treatment.

4. **Infection.** There is a potential that transfusions of white cells or T-lymphocytes may also serve as vectors of serious infection. All precautions to maintain sterility will be taken.

5. **Autoimmune Hemolytic Anemia.** Autoimmune hemolytic anemia has been reported in 2 out of 75 (2.6%) patients treated with CMV peptide-specific T-cells in prior phase 1 and phase 2 clinical study experience. Both SAEs were grade 3 events., and one event was considered possibly related to CMV peptide-specific T-cells while the other was considered to be unrelated. Patients who develop autoimmune hemolytic anemia should be managed per institutional standard.

Discussion with the medical monitor is encouraged.

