Our phase I trial of transplant donor-derived CMVpp65 peptide specific T-cells (05-065) has completed accrual and required follow up and is being readied for publication. Overall, 8/10 evaluable patients that had failed ganciclovir and/or foscarnet durably, cleared CMV viremia after single doses of 0.5, 1 or 2 x 10⁶ CMVpp65-CTLs/kg; all 46 patients treated with 3 weekly doses of 1 x 10⁶/kg CMVpp65 CTLs cleared CMV viremia. Elimination of CMV was consistently correlated with increments in circulating CMVpp65-CTL of the same epitope specificity and V β usage as the infused CMVpp65-CTL. Detectable numbers of CMVpp65 CTLs were sustained for 2-4 months. Acute toxicities were rare, no patient developed de novo GvHD.

We now propose a single-armed Phase II trial to evaluate transplant donor derived derived CMVpp65CTL in the treatment of CMV infections. This study will allow us to evaluate the ability of this treatment modality to prevent or limit the use of anti-viral drugs with their associated toxicities in patients treated with donor derived CMVpp65 T-cells.

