12.0 CRITERIA FOR THERAPEUTIC RESPONSE/OUTCOME ASSESSMENT

The primary endpoint of this study is to assess whether the infusion of the CMVpp65-CTLs has therapeutic activity in curing CMV infections in recipients of HSCT. This study specifically will evaluate the therapeutic efficacy and persistence after infusion of CMVpp65-CTLs derived from the HSCT transplant donor for the treatment of CMV infections. The second clinical end point of this study is the evaluation of GvHD induction after infusion of donor derived CMVpp65-CTLs. .

The responses of CMV infections will be clinically monitored as detailed under section 10. Responses to adoptively transferred T-cells are usually not observed until the T-cells have had time to expand within the transplant recipient, a period of at least 3 days, and as many as 18-21 days after the T-cell infusion. Accordingly, initial patient responses will be scored at weekly intervals, from day 7-day 21 post the initial infusion. Final responses will be captured in CRDB and scored between days 28-42 post the final infusion. Outcome responses will be captured post-first cycle and post final-cycle of infusions of CMV specific T cells. Best response observed in the full course of treatment will also be recorded as a distinct entity.

Clinical responses will be considered complete if all manifestations of CMV disease have resolved and/or the patient no longer has detectable CMV DNA by PCR.

A partial response will be defined as a $2 \times \log_{10}$ reduction in the level of CMV DNA detected in the patients blood and/or improvement in clinical parameters of CMV infection such that the patient is symptom-free.

Stable disease will be defined as no change in the clinic severity of disease in any organ.

Progressive disease will be defined as disease progression by clinical and radiologic parameters, ascribable to CMV infection in any affected organ, with unchanged or increased levels of CMV DNA.

Graft versus Host Disease initially developing after 10 days post T-cell infusion will be considered to be potentially ascribable to the T-cell infusion. Graft versus Host Disease will be diagnosed and clinically graded using the standard criteria of the IBMTR/NMDP Consensus Panel. Whenever, possible, the diagnosis will be confirmed by biopsy of skin or other involved organ, using the pathological criteria of Woodruff et al. Patients with preexisting GvHD of grade 1 severity not requiring

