17.2.2 Definition of SAE

An adverse event is considered serious if it results in ANY of the following outcomes:

- Death
- A life-threatening adverse event
- An adverse event that results in inpatient hospitalization or prolongation of existing hospitalization
- A persistent or significant incapacity or substantial disruption of the ability to conduct normal life functions
- A congenital anomaly/birth defect
- Important Medical Events (IME) that may not result in death, be life threatening, or require hospitalization may be considered serious when, based upon medical judgment, they may jeopardize the patient or participant and may require medical or surgical intervention to prevent one of the outcomes listed in this definition

Note: Hospital admission for a planned procedure/disease treatment is not considered an SAE.

SAE reporting is required as soon as the participant starts investigational treatment/intervention. SAE reporting is required for 30-days after the participant's last investigational treatment/intervention. Any event that occurs after the 30-day period that is unexpected and at least possibly related to protocol treatment must be reported.

Please note: Any SAE that occurs prior to the start of investigational treatment/intervention and is related to a screening test or procedure (i.e., a screening biopsy) must be reported.

The SAE report should be completed as per above instructions. If appropriate, the report will be forwarded to the FDA by the IND Office

Attribution:

- Unrelated: The AE *is clearly NOT related* to the intervention
- Unlikely: The AE *is doubtfully related* to the intervention
- Possible: The AE *may be related* to the intervention
- Probable: The AE *is likely related* to the intervention
- Definite: The AE *is clearly related* to the intervention

Expected and Unexpected Event:

- Expected: Any experience *previously reported* (in nature, severity, or incidence) in the current Investigator's Brochure or general investigational plan
- Unexpected: Any experience *not previously reported* (in nature, severity, or incidence) in the current Investigator's Brochure or general investigational plan

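### Apart from GvHD, a possibly related severe toxicity of a kind already reported need not be recorded more than 30 days after the last infusion

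*Combined protocol and SAP*

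**What the plan says.** Section 11.0 sets the toxicity window. The study will be "capturing and tracking Grade 3-5 toxicities which occur within 30 days following an infusion of CMV infusion CTLs", limited to events potentially attributable to study treatment. The next sentence exempts one toxicity: "We will also be capturing and tracking graft vs host disease occurring at any time point post-infusion". Patients stay evaluable until any donor lymphocytes, boost or second transplant.

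Section 17.2.2 sets the serious-event window: "SAE reporting is required for 30-days after the participant's last investigational treatment/intervention". For later events it says: "Any event that occurs after the 30-day period that is unexpected and at least possibly related to protocol treatment must be reported". It classes an event as expected or unexpected by whether it was previously reported "in nature, severity, or incidence) in the current Investigator's Brochure or general investigational plan".

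Section 11.0, item 5, states: "Autoimmune hemolytic anemia has been reported in 2 out of 75 (2.6%) patients treated with CMV peptide-specific T-cells". Both cases were Grade 3 SAEs; one was judged possibly related and the other unrelated.

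Section 3.0 says of the phase I experience: "Detectable numbers of CMVpp65 CTLs were sustained for 2-4 months". Section 10.0 and its schedule table provide history, physical examination, CBC and metabolic panel weekly to week 8 and then about monthly to month 6. Footnote 2 of the table restarts the calendar with each further cycle.

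**The concern.** For toxicities other than GvHD, the two collection rules leave a gap between them. Section 11.0 stops at 30 days. After that, Section 17.2.2 picks up only events that are new in kind, severity or frequency. A late event that looks like one already seen, and that the investigator thinks may be due to the cells, falls under neither rule.

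This matters because the product is living cells that, on the protocol's own account, remain detectable well beyond 30 days. The protocol already accepts that one cell-mediated harm, GvHD, can arise late and must be followed without a time limit. It also scores response beyond 30 days: "Final responses will be captured in CRDB and scored between days 28-42 post the final infusion". At stake is how complete the safety summary is for hazards the sponsor already knows about. The visits at which such events would be found are already in the schedule.

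**Working it through.** **1. Following one event through the rules.** Take a possibly related Grade 3 autoimmune hemolytic anemia on day 45 after the last infusion.

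- Section 11.0 toxicity capture: 45 > 30, so it is outside the window.
- Section 11.0 GvHD exception: not GvHD, so it does not apply.
- Section 17.2.2, first 30 days: outside the window.
- Section 17.2.2, after 30 days: the event is possibly related, but it must also be unexpected. Its nature and severity match the earlier cases in Section 11.0, item 5. Unless its incidence is judged to be new, it is expected and need not be reported.

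**2. When capture ends.** Inputs: infusions on days 0, 7 and 14 (schedule table) and a 30-day window (Section 11.0). For one on-time course, 14 + 30 = day 44 from the first infusion. Further courses move this date later, but the window still closes 30 days after the last infusion.

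**3. Share of the persistence period left uncovered.** Input: 2-4 months (Section 3.0), or about 61-122 days at 30.44 days per month. The protocol does not say from which infusion this is counted, so both origins are shown.

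| Persistence counted from | 2 months | 4 months |
|---|---|---|
| First infusion | (61 − 44)/61 = 28% | (122 − 44)/122 = 64% |
| Last infusion | (61 − 30)/61 = 51% | (122 − 30)/122 = 75% |

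**4. Visits after the window.** Weeks 7 and 8 (days 49 and 56) and months 3, 4, 5 and 6 fall after day 44. That is 6 of the 14 on-study columns. All six include history, examination, CBC and metabolic panel.

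**5. How likely an event of this kind is.** The protocol's figure is 2/75 = 2.67%, printed as 2.6%. The gap concerns possibly related events, so the relevant numerator is the one case so judged: 1/75 = 1.33%. The chance of at least one in n patients is 1 − (74/75)^n.

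- n = 7, the additional accrual expected after Amendment 22 (Section 14.0): 1 − (74/75)^7 = 0.090.
- n = 15, the total in Section 14.0's confidence-interval illustration: 1 − (74/75)^15 = 0.182.

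These are chances of a case at any time. The documents give no onset times, so the share falling after the window could be anything from 0 to 100%.

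**The case against.** The strongest reply is that the gap is narrow. GvHD is the safety question in the primary objectives and the only toxicity with a stopping rule, and it is tracked without a time limit. A reader might infer from the 30-day limit that late events of every kind named in Section 11.0 go uncollected; the GvHD sentence rules that out.

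Unexpected also covers severity and incidence. A Grade 4 case would differ in severity from the earlier ones. With so few patients, even one case could be argued to exceed past incidence (1/7 = 14%, against 2.6%). The Investigator's Brochure is not among the documents, and several Section 11.0 risks are described as possibilities rather than as events that have occurred. So the example is secure only for autoimmune hemolytic anemia. This part of the reply stands. But it makes late capture depend on a judgement about incidence for which the protocol gives no rule.

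Patients are still seen to month 6, and item 5 encourages discussion with the medical monitor. Surveillance is therefore not missing. What is missing is a requirement to record what is found.

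Finally, detectable cells do not show a constant hazard, and Section 11.0 expects antiviral effects over days to weeks. This also stands, and it is why no estimate of missed events is offered.

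**Conclusion.** The gap is in the text and is worth closing. It is a weakness of design and does not contradict any stated figure. Apart from GvHD, a possibly related Grade 3-5 toxicity of a kind, severity and incidence already reported need not be recorded once 30 days have passed since the last infusion. For a single on-time course this leaves about 28-64% of the stated persistence period uncovered, or about 50-75%, depending on the origin. The chance of at least one possibly related hemolytic anemia at any time is about 9% in 7 patients and 18% in 15. This assumes that the 1/75 experience carries over and that the earlier cases make such an event expected.

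Three stronger readings are tempting, and the documents do not support them:

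- That half or more of such events would be missed. This needs onset spread evenly over the persistence period, and no onset data are given.
- That the toxicity rate is biased. Section 14.0 plans no overall toxicity-rate estimate, and a rate defined to day 30 is limited in scope rather than wrong.
- That the monitoring committee would not receive these events. Section 16.3 does not say which events it receives.

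**What to change.** - **Section 11.0:** extend capture of Grade 3-5 toxicities at least possibly related to the CTLs to the month-6 visit of the last course. Keep the existing evaluability cut-off at donor lymphocytes, boost or second transplant, and leave the current 30-day attribution wording otherwise unchanged.
- **Section 17.2.2:** reword the late-event sentence so that, after 30 days, any SAE at least possibly related is recorded whether or not it was expected.
- **Reporting:** present toxicity separately for up to day 30 and after day 30 from the last infusion, so that the early figure stays comparable with the present definition.

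For a single course, month 6 is about day 183, so capture gains about 183 − 44 = 139 days and uses six visits already scheduled. The cost is protocol wording, a few more case-report entries, and possibly a slightly higher reported toxicity rate. No visit or test is added, and neither treatment nor the stopping rule changes.
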